**Table 3-2 Study drug dose levels for sacubitril/valsartan**

age groups 1 and 2 *	
Dose levels for pediatric formulation	
Dose level 1	0.8 mg/kg bid.
Dose level 2	1.6 mg/kg bid.
Dose level 3	2.3 mg/kg bid.
Dose level 4	3.1 mg/kg bid.
Dose levels for adult formulation	
Dose level 1	50 mg bid.
Dose level 2	100 mg bid.
Dose level 3	150 mg bid.
Dose level 4	200 mg bid.

\*Note: sacubitril/valsartan target dose (dose level 4) for age groups 1 and 2 is 3.1 mg/kg bid. (see [Section 4.2](#) for additional details).

If a subject is unable to tolerate up-titration to a higher sacubitril/valsartan dose level or at the discretion of the investigator, subjects may be maintained on lower dose levels of sacubitril/valsartan (dose level 1-3, see [Table 3-2](#)). In case of a consecutive 3-month interruption of study treatment, subject should be discontinued from the study and should complete Visit 599.

An outline of the study design is presented in [Figure 3-1](#). Depending on when and where the patient is enrolled, the duration of the study varies from 1 to approximately 4.5 years.

The OLE study drug starting dose will depend either upon the dose of ACEI/ARB that the subject was transitioned to after completion of the PANORAMA-HF or the dose the subject was on at the End of Study visit for the core study PANORAMA-HF prior to screening (Visit 500; refer to [Table 3-2](#)).

At Visit 501, subjects who meet eligibility criteria will start the study drug at dose level 1 or 2 ([Table 3-2](#)). Subjects who were on dose level 1 at the PANORAMA-HF End of Study (PANORAMA-HF visit 416) or who are on a low dose of ACEI/ARB (dose levels 1; [Table 3-3](#)) or not on an ACEI/ARB prior to screening (Visit 500) should start at dose level 1 at Visit 501.

[figure not shown]
Subjects who were on dose level 2, 3 or 4 at PANORAMA-HF visit 416 or who are on a higher dose of ACEI/ARB (dose levels 2, 3 or 4; [Table 3-3](#)) prior to screening (Visit 500) should start at dose level 2 at Visit 501 ([Table 3-2](#)) or at dose level 1 at investigator's discretion.

During the study, visits to assess safety will be conducted at Visit 501 and at 3-months intervals until the conclusion of the study (except for titration visits, which are at 2-week intervals). Unscheduled visits are allowed for subject's safety and for dose adjustment purposes

**Table 3-3 Total daily dose levels of commonly prescribed ACEI/ARBs for the purpose of comparing to dose levels of study drug**

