Dose level 3	2.3 mg/kg bid.	4.6 mg/kg/day
Dose level 4	3.1 mg/kg bid.	6.2 mg/kg/day
Dispensing dose levels for adult formulation		Weight based daily dose
Dose level 1	50 mg bid.	1.6 mg/kg/day
Dose level 2	100 mg bid.	3.2 mg/kg/day
Dose level 3	150 mg bid.	4.6 mg/kg/day
Dose level 4	200 mg bid.	6.2 mg/kg/day

*Note: sacubitril/valsartan target dose (dose level 4) for age groups 1 and 2 is 3.1 mg/kg bid.

Table 2-2 Tablet use for sacubitril/valsartan (43 to < 57 kg patients)

Study drug	Pediatric dose level	Patient weight (kg)	Pediatric dose	Tablet dose
LCZ696	Dose level 4	43 to < 57 kg	>= 133 to < 177 mg	150 mg
	Dose level 3	43 – 54 kg	>= 98 to <125 mg	100 mg
	Dose level 3	>54 to <57 kg	>= 125 to < 131 mg	150 mg

Dispensing level (dose level) and daily dose at each visit

For a given visit, the visit associated dosing interval is defined as the dosing interval with its start date prior to or equal to the date of visit AND its end date later than or equal to the date of visit; the dose level and weight based daily dose (mg/ kg/day) at the visit are defined as the dose level and weight based daily dose (mg/kg/day) for the visit associated dosing interval. In the case that, the visit date is equal to the end date of an earlier dosing interval as well as the start date of a later dosing interval, the later dosing interval will be taken as the visit associated dosing interval.

The dose level will be summarized by visit, for overall and for each age group, using the number and percentage of patients on each level; and further be summarized using number of observations, mean, standard deviation, median, minimum, Q1, Q3, and maximum; the weight based daily dose (mg /kg/day) will be summarized by visit, for overall and for each age group, using number of observations, mean, standard deviation, median, minimum, Q1, Q3, and maximum.

The summary will include all scheduled visits in the study or until treatment discontinuation date.

Duration of treatment exposure

Duration of exposure to treatment regardless of temporary interruptions is defined as: date of last dose of study treatment – date of first dose of study treatment + 1.

Conversion for treatment exposure durations is as follows:

- 1 week = 7 days
- 1 month = 30.4375 days
- 1 year = 365.25 days

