Total (sum of patient-years) and per-patient duration of exposure to the study treatment will be summarized for each age group and for overall in years, using mean, standard deviation, median, Q1, minimum, Q3 and maximum.

The duration (day) of treatment exposure excluding study drug interruptions is defined as the sum of the duration (day) on dose level 1 to 4 during the study without counting any days that patients are not taking the treatment.

The analyses specified in the Section “Dispensing level (dose level) and daily dose at each visit” will be used here. In addition, the duration of study drug exposure with and without study drug interruptions, respectively, will be categorized into:

- < 6 months
- 6 months to < 1 year
- 1 to < 2 years
- 2 to < 3 years
- 3 to < 4 years
- >=4 years.

The number and percentage of patients within each category by age group and overall will be tabulated.

Duration on each dose level

For a given dose level, the duration (day) on this dose level is defined as the number of days on this dose level during the period from the date of the first dose of the study drug to the date of the last dose of the study drug. In the case that the end date of an earlier dosing interval is the same as the start date of a later dosing interval, the day will be counted as 0.5 day on both the earlier dose level and the later dose level. In the case that the date of permanent discontinuation of the study drug is the same as the date of the last dose of the study drug, the day will be counted as 0.5 day on the dose level of the last dose but not counted on dose level 0.

The median and interquartile range will be presented for duration on each dose level. The number of patients who have ever been on a specific dose level will be reported.

Time to permanent discontinuation of the study drug

The time (day) to permanent discontinuation of the study drug during the study (excluding death) will be summarized for each age group and overall by duration categories (refer to the Section “Duration of study drug exposure” for specific categories) using the Kaplan-Meier curves, considering time-to-death, completion of the study and switch to commercial entresto as independent censoring.

Mean weight based daily dose and mean dose level

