2.8.1 Adverse events (AEs)

All AEs will be identified using Medical Dictionary for Regulatory Activities (MedDRA). The MedDRA version used for reporting the study will be described in a footnote.

An AE with its severity increased should be considered and recorded as a new AE.

Treatment emergent adverse events (TEAEs) are defined as any recorded AE with its start date-time (recorded or imputed) on or after the start date-time of the treatment period and end date as the end date of the treatment period or the date of last dose taken as reported in the DAR page + 30 days. Any AE happening after treatment discontinuation +30 days but still within the study period (e.g., where patient did not discontinue the study on the same date of treatment discontinuation) would not be considered as a TEAE and will be reported in the listing of AE.

The following adverse events will be summarized by primary system organ class, preferred term, and maximum severity as appropriate, for each age group and for overall, using numbers and percentages of patients with at least one adverse event in the corresponding class (see list below). Outputs will be produced for AEs regardless of study-drug relationship, and for study-drug related AEs. Study drug related AEs are defined as any recorded AE with “Reasonable possibility that AE is related to study treatment” answered as “YES”. Serious adverse events (SAEs) are defined as any recorded AE with “Does AE meet the definition of an SAE” answered as “Yes”.

Adverse events summaries

- Any adverse event (treatment emergent or not)
- Any serious adverse event (treatment emergent or not)
- Treatment emergent adverse event (TEAE)
- Treatment emergent serious adverse event
- Treatment emergent adverse event (TEAE) occurred in >5% of patients
- Treatment emergent serious adverse event (TESAE) occurred in >5% of patients

- Treatment emergent adverse event of special interest, e.g. angioedema (both, adjudicated and non-adjudicated), change in bone growth and density, cognitive impairment (narrow SMQ), embryo-fetal toxicity or lethality, hepatotoxicity, hyperkalemia, hypersensitivity, hypotension, malignancy, neonatal or infantile toxicity through exposure from breast milk, renal impairment (narrow SMQ), and/or statin drug interaction as defined in the Case Retrieval Sheet for LCZ696 (see [Section 2.8.1.1](#))

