- TEAE and TESAE leading to dose adjustment, temporary dose interruption, or permanent discontinuation (including death) of study treatment
- TEAE and TESAE leading to permanent discontinuation (including death) of study treatment
- TEAE and TESAE leading to death

The following rules are applicable to the summaries:

- If a patient reported more than one AE with the same PT, the patient will be counted only once with the greatest severity at the PT level
- If a patient reported more than one AE within the same SOC, the patient will be counted only once with the greatest severity at the SOC level, where applicable.

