2.8.1.1 Adverse events of special interest / grouping of AEs

Most common TEAEs are defined as any recorded TEAE corresponding to a PT with at least 5% of patients having at least one TEAE of this PT. Most common TEAEs will be derived overall and by age group and will be summarized by age group and for overall, by SOC and PT, in descending frequency according to incidence, starting from the most common event.

[Table 2-1](#) shows the identified and potential risks for LCZ696 and the specifically specified analyses for each risk. In addition, the following standard analyses will be applied to all risks.

- Numbers and percentages of patients with any TEAE within the risk category (or SOC/PT within risk category) by age group and risk category, SOC, PT and maximum severity.
- Exposure adjusted incidence rates per 100 patient-years for TEAEs within the risk category by age group and risk category.
- Listing of patient numbers per risk.

Table 2-3 Identified and potential risks

Risk	Analysis
Hyperkalemia	1. Standard analyses; 2. Numbers and percentages of patients with treatment emergent hyperkalemia among patients with/without hyperkalemia at baseline by age group and overall 3. Numbers and percentages of patients with any post-baseline serum potassium ≥ 5.5 mEq/L, >6.0 mEq/L and >6.5 mEq/L by age group and overall
Hypotension	1. Standard analyses;

Risk	Analysis
	
2. Blood pressures and change from baseline in blood pressures will be summarized by visit, time point, age group and overall using number of observations, mean, standard deviation, median, minimum, Q1, Q3, and maximum;
 
3. Numbers and percentages of patients with the following events during the treatment period will be provided by age group and overall:
 
• Post-baseline systolic blood pressure (SBP) < 5th percentile per age (Table 16-7 in the protocol);• At least 20 mmHg drop in SBP (post-baseline assessments comparing to baseline);• Simultaneous treatment emergent symptomatic hypotension and postbaseline SBP < 5th percentile per age (Table 16-7 in the protocol);• Simultaneous treatment emergent symptomatic hypotension and at least 20 mmHg drop in SBP (post-baseline assessments comparing to baseline);• Simultaneous post-baseline SBP < 5th percentile per age (Table 16-7 in the protocol) and at least 20 mmHg drop in SBP (post-baseline assessments comparing to baseline).
Angioedema (positively adjudicated events)	Standard analyses;

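### One pooled exposure-adjusted rate per special-interest risk, with no formula given, mixes the 8-week titration phase with up to about 4.5 years of follow-up and could understate the risk at the start of treatment

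*SAP*

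**What the plan says.** SAP 2.8.1.1 lists three standard analyses for all identified and potential risks: patients with an event as n (%), "Exposure adjusted incidence rates per 100 patient-years for TEAEs within the risk category by age group and risk category", and a listing. The rate has no formula. The SAP does not say whether the numerator is patients or events, whether person-time stops at the first event, or which exposure is the denominator.

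SAP 2.4.1 defines two durations. One runs from first to last dose: "Duration of exposure to treatment regardless of temporary interruptions is defined as: date of last dose of study treatment" minus the date of first dose, plus 1. The other leaves out interruptions: "The duration (day) of treatment exposure excluding study drug interruptions is defined as the sum of the duration (day) on dose level 1 to 4". It also says "Total (sum of patient-years) and per-patient duration of exposure to the study treatment will be summarized". Neither duration is tied to the event rate.

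SAP 2.8.1 counts an event as treatment-emergent up to the end of the treatment period or "the date of last dose taken as reported in the DAR page + 30 days". For the n (%) summaries, "the patient will be counted only once with the greatest severity at the PT level", with a matching rule by system organ class. The SAP does not say that these rules carry over to the rate.

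Protocol Section 3 says that "the duration of the study varies from 1 to approximately 4.5 years". Protocol 4.2 and 6.1.4 tie the length to local authorisation, commercial availability, local limits and the calendar end of the study. Visits 502 to 505 (Weeks 2 to 8) are for up-titration.

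**The concern.** An exposure-adjusted rate is meant to make groups with unequal follow-up comparable. It does so only if the hazard is about constant. If risk is concentrated early, each added year of low-risk maintenance dilutes the rate, and the result depends on how long a child could stay in the study. Here that length is largely set by country and enrolment date, which are not properties of the drug.

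The protocol gives reasons to doubt constant risk for three of the listed risks. Section 6.5.1 names hyperkalemia, symptomatic hypotension and renal dysfunction as the focus of dose-level adjustment. Section 3 starts every child at dose level 1 or 2 and titrates upward over the first weeks. Sections 6.5.1 and 9.1.1 take children who permanently stop the drug out of the study, so later person-time comes from those who tolerate it.

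The study's only objective is long-term safety and tolerability, and this rate is the only planned adjustment for follow-up on special-interest adverse events. Kaplan-Meier curves are planned only for permanent discontinuation of study drug (SAP 2.4.1). If the pooled rate is low because it is mostly maintenance time, a reader could take it as the risk faced by a child who is starting treatment.

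**Working it through.** **No figure to reproduce.** Neither document gives an event rate or hazard for these risks, and no sample size is set. The hazards below are assumptions, varied to show the range.

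**Inputs from the documents**
- Follow-up T: 1 year and 4.5 years (Protocol Section 3). These are planned lengths. Observed exposure is not given.
- Titration: Weeks 2 to 8 (Protocol Table 8-1).
- Tail after last dose: 30 days (SAP 2.8.1). Year: 365.25 days (SAP 2.4.1).

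**Assumed:** hazard h1 per patient-year up to 0.25 year, then h2.

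**Formulas**
- Probability of a first event by T: P = 1 − exp(−0.25·h1 − (T − 0.25)·h2).
- Reading A, first events over whole exposure: 100·P/T.
- Reading B, first events over time at risk: 100·P/R, where R = (1 − exp(−0.25·h1))/h1 + exp(−0.25·h1)·(1 − exp(−(T − 0.25)·h2))/h2.

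**Worked case, h1 = 0.60, h2 = 0.05**
- T = 1: P = 1 − exp(−0.15 − 0.0375) = 0.1710. A = 17.1. R = 0.2322 + 0.6336 = 0.8657. B = 19.75.
- T = 4.5: P = 1 − exp(−0.15 − 0.2125) = 0.3041. A = 0.3041/4.5 = 6.8 per 100 patient-years. R = 0.2322 + 3.2955 = 3.5276. B = 8.62.

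**Rates per 100 patient-years**

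| Hazard to 3 months, then after | A: 1 y | A: 4.5 y | Ratio A | B: 1 y | B: 4.5 y | Ratio B |
|---|---|---|---|---|---|---|
| 10, 10 | 9.52 | 8.05 | 1.18 | 10.0 | 10.0 | 1.00 |
| 20, 10 | 11.75 | 8.40 | 1.40 | 12.62 | 10.69 | 1.18 |
| 60, 5 | 17.10 | 6.76 | 2.53 | 19.75 | 8.62 | 2.29 |

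Within a row, the 1-year and 4.5-year children have identical risk at every time point.

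**What the table separates.** Two mechanisms are at work. Counting time after the first event explains the whole gap in row 1 and little of it in row 3. Falling hazard explains most of row 3, and stopping person-time at the first event does not remove it.

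**Limits of the ratio.** With all events as numerator and a constant rate, the ratio is 1.00. With no risk left after the early phase, it reaches 4.5 under reading A.

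**What a split rate gives.** In row 3 the early rate is P(0.25)/R(0.25) = 0.1393/0.2322 = 60 per 100 patient-years. The later rate is 5. Both hold whatever the length of follow-up.

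**Tail.** If the 30 days count in the numerator only, the omitted time is 30/365.25 = 8.2% of a 1-year denominator and 8.2/4.5 = 1.8% of a 4.5-year one.

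**The case against.** The case for leaving the plan alone has several parts.

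- **The SAP does not state the faulty method.** A reader might infer that the rate divides by whole exposure and keeps counting after the first event, because total patient-years is a defined quantity and patients are counted once in the n (%) tables. The documents do not say so. They define two exposure durations, and the counting rules are written for other tables. If the rate counts all events, keeping later time is correct. This stands.
- **The front-loading is plausible, not shown.** Apart from those stopped by the urgent safety measure, entrants were on core-study drug at its last visit (Protocol 5.1), and some had already taken sacubitril/valsartan (Protocol 6.3.2). That may soften early risk. Titration also gives no reason to expect early risk for malignancy, cognitive impairment or bone growth. This stands, so the point is confined to three risks.
- **Early risk is partly visible elsewhere.** Blood pressure, creatinine, eGFR, laboratory shifts and notable vital signs are tabulated by visit, including the titration visits (SAP 2.8.1.1, 2.8.3, 2.8.4.2). This stands in part: those tables show measurements and not the incidence of special-interest adverse events over time.
- **The study is descriptive.** Nothing is tested, and no table compares 1-year with 4.5-year participants. This is true, but the rates will still be read as risk estimates, and by age group.

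**Conclusion.** The concern holds in a limited form. The planned rate is undefined, and one pooled figure per risk cannot separate the risk of starting treatment from the risk of staying on it. For hyperkalemia, hypotension and renal impairment, the protocol itself gives reason to doubt constant risk. No other planned analysis shows the incidence of these adverse events over time.

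The size is conditional. Under reading A the ratio of the 1-year to the 4.5-year rate is 1.18, 1.40 or 2.53 for the three sets of assumed hazards, and the possible range is about 1.0 to 4.5. A reader might take the 2.5-fold figure as a property of the design. It is not: it needs an early hazard 12 times the later one (60/5), and neither document supports or excludes that.

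A reader might also infer that false age-group differences will appear. They could, if follow-up differs between the groups. The documents give no follow-up by age group, so neither the presence nor the size of such a difference can be established.

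**What to change.** In SAP 2.8.1.1, define the rate as patients with a first event divided by the summed time to first event or end of the treatment-emergent window. Handle the 30 days after last dose the same way in numerator and denominator, and state whether interruptions count as time at risk.

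At least for hyperkalemia, hypotension and renal impairment, report the rate separately for an early period that covers titration and for the time after, by age group and overall, with exact Poisson 95% intervals. The first 3 months is one workable early period. The cut is a choice, and it should be fixed before the data are analysed.

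This needs no new data, only SAP wording and slightly more programming. The downsides are sparser cells, with wide intervals in the smaller age group, and early-period rates that may look higher than the pooled rate.

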**Table 16-6 GFR by age for initiation/up-titration and exclusion criteria**

Age range*	$\geq 30\%$ mean GFR for age (mL/min/1.73m  )**	< 30% mean GFR for age (mL/min/1.73m  )***
12 months to < 19 months (1 year, 7 months)	$\geq 31$	< 31
19 months to < 18 years	$\geq 38$	< 38
$\geq 18$ years	$\geq 30$	< 30

\* Age rounded to nearest whole number

\*\* Initiation/up-titration criteria

\*\*\* Exclusion criteria

Source: ([Peters and Gordon 1999](#))

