Renal impairment	
1. Standard analyses;
 
2. For serum creatinine and eGFR, the test values and changes from baseline will be summarized by visit, age group and overall using number of observations, mean, standard deviation, median, minimum, Q1, Q3, and maximum; the summaries will be provided for local and central lab separately;
 
3. Numbers and percentages of patients with the following events will be provided by age group and overall (the summaries will be provided for local and central lab together and if both central lab and local lab data are available, central lab result will take precedence over local lab result):
 
• eGFR decline by >25%, >40%, >50%, and/or >30 mL/min/1.73 m² (postbaseline assessments comparing to baseline) and <LLN;• eGFR < 45 mL/min/1.73 m² and/or eGFR < 30 mL/min/1.73 m²• Serum creatinine increase by >50% (post-baseline assessments comparing to baseline) and >ULN;• Serum creatinine increase by >0.5 mg/dL and >ULN (post-baseline assessments comparing to baseline),• serum creatinine post-baseline >2.0 mg/dL, >2.5 mg/dL, >3.0 mg/dL ;• Standard analyses within the subgroups additionally if possible: patients with baseline eGFR ≤170 mL/min/1.73 m² and >170 mL/min/1.73 m².

For safety topics of special interest defined in the CRS, the standard analyses will be performed.

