White Blood Cell Count	x10E3/uL	>50% increase and >ULN; >50% decrease and <LLN.	x10E9/L
Platelet Count	x10E3/uL	>75% increase and >ULN; >50% decrease and <LLN.	x10E9/L
Chemistry			

BUN	mg/dL	>50% increase and >ULN	mmol/L
Creatinine	mg/dL	>50% increase and >ULN	umol/L
Albumin	g/dL	<20	g/L
Glucose	mg/dL	>50% increase and >ULN; (>50% decrease and <LLN) or any value <3.3.	mmol/L
Total Bilirubin	mg/dL	>100% increase and >ULN	umol/L
AST (SGOT)	U/L	>150% increase and >ULN	U/L
ALT (SGPT)	U/L	>150% increase and >ULN	U/L
Sodium	mEq/L	(>5% increase and >ULN) or any value >150; (>5% decrease and <LLN) or any value <125	mmol/L
Potassium	mEq/L	(>20% increase and >ULN) or any value >6; (>20% decrease and <LLN) or any value <3.	mmol/L
Chloride	mEq/L	>10% increase and >ULN; >10% decrease and <LLN	mmol/L
Calcium	mg/dL	>10% increase and >ULN; >10% decrease and <LLN.	mmol/L
Uric Acid	mg/dL	>50% increase and >ULN	mmol/L

Liver events

[Table 2-4](#) provides criteria for liver laboratory triggers and liver events.

The liver laboratory triggers and liver events during the treatment period based on the local laboratory assessments and the central laboratory assessments will be summarized together by criteria and age group, using the numbers and percentages of patients satisfying such criteria.

Table 2-6 Liver event and laboratory trigger definitions

Definition / threshold	
LIVER LABORATORY TRIGGERS	
 • $3 \times \text{ULN} < \text{ALT} / \text{AST} \leq 5 \times \text{ULN}$ • $1.5 \times \text{ULN} < \text{TBL} \leq 2 \times \text{ULN}$
LIVER EVENTS	
 • ALT or AST $> 5 \times \text{ULN}$ • ALP $> 2 \times \text{ULN}$ (in the absence of known bone pathology) • TBL $> 2 \times \text{ULN}$ (in the absence of known Gilbert syndrome) • ALT or AST $> 3 \times \text{ULN}$ and INR > 1.5 • Potential Hy's Law cases (defined as ALT or AST $> 3 \times \text{ULN}$ and TBL $> 2 \times \text{ULN}$ [mainly conjugated fraction] without notable increase in ALP to $> 2 \times \text{ULN}$) • Any clinical event of jaundice (or equivalent term) • ALT or AST $> 3 \times \text{ULN}$ accompanied by (general) malaise, fatigue, abdominal pain, nausea, or vomiting, or rash with eosinophilia • Any adverse event potentially indicative of a liver toxicity*

Definition / threshold

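### Several fixed-threshold safety counts do not separate patients who already met the threshold at baseline from patients who newly cross it on treatment

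*SAP*

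**What the plan says.** SAP Section 2.8.1.1, Table 2-3, lists patient counts against fixed limits:

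- Renal: "eGFR < 45 mL/min/1.73 m² and/or eGFR < 30 mL/min/1.73 m²" and "serum creatinine post-baseline >2.0 mg/dL, >2.5 mg/dL, >3.0 mg/dL".
- Hypotension: "Post-baseline systolic blood pressure (SBP) < 5th percentile per age".
- Hyperkalemia: "Numbers and percentages of patients with any post-baseline serum potassium ≥ 5.5 mEq/L, >6.0 mEq/L and >6.5 mEq/L".

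SAP Section 2.8.3 reports the liver triggers and events of Table 2-6 as "summarized together by criteria and age group, using the numbers and percentages of patients satisfying such criteria". Its notable laboratory criteria (Table 2-5) mostly require a change from baseline plus an out-of-range value. They also contain a fixed albumin limit and any-value limits for hemoglobin, glucose, sodium and potassium, which need no change. SAP Section 2.8.4.2 counts patients beyond the Table 2-7 vital-sign limits, by visit.

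None of these rows is conditioned on baseline status. The SAP does condition elsewhere: urine events must be new onset (Section 2.8.3), and treatment-emergent hyperkalemia is reported separately for patients with and without hyperkalemia at baseline (Table 2-3).

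**The concern.** There is one treatment arm (Protocol Section 6.1.3), and laboratory values and vital signs are primary endpoints (Protocol Section 12.4.1; SAP Section 2.5.1). With no comparator, nothing offsets the patients who entered with the abnormality. A child who enters with eGFR 40 and is later measured at 44 has improved by 10%, yet is listed among the renal impairment events. Where eligible patients can start beyond a limit, the percentage blends baseline prevalence with new on-treatment findings, and the reader cannot tell the two apart.

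The eGFR bullet has a further gap: it is not restricted to post-baseline values, although the creatinine bullets beside it are. The SAP starts the treatment period on the date of first dose (Section 2.1.1). A pre-dose sample taken that day falls inside the period by date.

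**Working it through.** There is no planned figure to reproduce. The check is whether an eligible patient can already meet each limit at baseline.

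**eGFR.** Exclusion criterion 5 (Protocol Section 5.2) and Protocol Table 16-6 set the lowest eligible values: 31 from 12 to under 19 months, 38 in the band "19 months to < 18 years", and 30 at 18 years and over.

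- Below 45: reachable in every band, at 31-44, 38-44 and 30-44. With eGFR = 0.413 × height / creatinine (Protocol Appendix 3), a 150 cm child has 0.413 × 150 = 61.95. An eGFR of 38 to under 45 is then a creatinine above 61.95/45 = 1.38 and up to 61.95/38 = 1.63 mg/dL.
- Below 30: not reachable in any band.

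**Creatinine.** The height needed to stay eligible is minimum eGFR × creatinine / 0.413. From 19 months to under 18 years:

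- Above 2.0 mg/dL: 38 × 2.0 / 0.413 = 184 cm, so only very tall patients.
- Above 2.5 mg/dL: 38 × 2.5 / 0.413 = 230 cm, not realistic.
- Above 3.0 mg/dL: 38 × 3.0 / 0.413 = 276 cm, not realistic.

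Under 19 months, even 2.0 mg/dL needs 31 × 2.0 / 0.413 = 150 cm. At 18 and over an adult formula applies that the documents do not state, so the limits cannot be checked there.

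**Liver.** Exclusion criterion 5 bars ALT or AST above 3 × ULN. That removes the 3-5 × ULN trigger, >5 × ULN, the INR combination, Hy's Law and the symptom criterion. Bilirubin above 1.5 or 2 × ULN and ALP above 2 × ULN have no entry limit.

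**Table 2-5 fixed limits.** There is no entry limit for albumin <20 g/L, hemoglobin <70 g/L, glucose <3.3 mmol/L, sodium >150 or <125 mmol/L, or potassium <3 mmol/L.

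**Potassium ≥5.5 and above, and SBP below the 5th percentile.** Section 5.2 sets no limit. Protocol Table 3-1 requires serum potassium ≤5.4 mmol/L and SBP above the 5th percentile, and its title covers initiation as well as up-titration. The text of Protocol Section 3 applies it before the next higher dose level, during up-titration. If the title governs, neither row should be met at the first dose. If the text governs, both can be.

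**Table 2-7.** Heart rate has no entry limit. For low SBP, even if Table 3-1 binds at Visit 501:

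| Age (years) | 5th percentile, Protocol Table 16-7 | Notable if below, SAP Table 2-7 | Passes Table 3-1 but notable (mmHg) |
|---|---|---|---|
| 1 | 72 | 76 | 73-75 |
| 2 | 74 | 76 | 75 |
| 3 | 76 | 82 | 77-81 |
| 4 | 78 | 82 | 79-81 |
| 5 | 80 | 82 | 81 |
| 6 | 82 | 90 | 83-89 |
| 7 | 84 | 90 | 85-89 |
| 8 | 86 | 90 | 87-89 |
| 9 | 88 | 90 | 89 |
| 10-17 | 90 | 90 | none |

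**How the mixing works (assumed inputs only).** Let b be the share beyond the limit at baseline, r the chance that such a patient is beyond it again on treatment, and q the proportion newly crossing among the rest. The reported proportion is b·r + (1−b)·q. Take b = 1-5% and r = 0.5-0.9:

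- q = 2%: from 0.01 × 0.5 + 0.99 × 0.02 = 2.5% to 0.05 × 0.9 + 0.95 × 0.02 = 6.4%. Pre-existing cases are 20% to 70% of those counted.
- q = 5%: from 0.01 × 0.5 + 0.99 × 0.05 = 5.45% to 0.05 × 0.9 + 0.95 × 0.05 = 9.25%. Pre-existing cases are 9% to 49%.

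Where entry criteria force b = 0, conditioning changes nothing.

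**The case against.** The strongest reply is that counting any on-treatment value beyond a fixed limit is a legitimate description, and that baseline is handled next to it. Table 2-3 also has eGFR declines and creatinine increases from baseline, an SBP drop of at least 20 mmHg, and a row combining that drop with SBP below the 5th percentile. Low/normal/high laboratory shift tables are planned. The isolated bilirubin and ALP criteria set aside known Gilbert syndrome and known bone pathology. This stands in part: the plan does look at change. But none of these outputs shows who newly crossed eGFR 45, 2 × ULN bilirubin or a Table 2-7 limit. The shift tables use reference-range categories rather than these cut-offs, and none is planned for vital signs. The baseline eGFR subgroup splits at 170, which does not isolate low entrants.

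Four stronger readings are tempting and not supported:

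- *Every fixed-limit row is affected.* It is not. eGFR below 30 and the numeric ALT/AST criteria are barred at entry, and creatinine above 2.5 or 3.0 mg/dL is not realistically reachable under 18.
- *Every entrant below 45 is automatically an event.* Laboratory data are reported for the treatment period, so apart from a same-day pre-dose sample a low value must recur on treatment.
- *The SAP presents these counts as incidence.* It calls them numbers and percentages of patients. Exposure-adjusted rates are specified only for adverse events, and Table 2-7 counts are by visit.
- *The SBP share can be sized from an assumed normal distribution.* The spread and the shift from the reference mean would both be invented. The calculation would ignore Table 3-1, and the note to Protocol Table 16-7 says its formula generally gives a lower value than the population percentile.

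**Conclusion.** The point holds for a defined set of rows:

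- eGFR below 45;
- bilirubin above 1.5 or 2 × ULN, and ALP above 2 × ULN;
- the albumin limit and the any-value limits for hemoglobin, glucose, sodium and low potassium;
- the Table 2-7 limits, namely heart rate and, at about ages 1 to 9, low SBP;
- possibly creatinine above 2.0 mg/dL in adult or very tall patients.

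Potassium ≥5.5, >6.0 and >6.5 and SBP below the 5th percentile join the list only if Table 3-1 does not bind at Visit 501, and the protocol is unclear on that. Even if it binds, the protection is incomplete. Visit 501 laboratory tests are at the investigator's judgement (Protocol Section 8.1). A local value may satisfy the criterion while the central value is taken as baseline (SAP Section 2.1.1).

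The direction is clear: pre-existing cases can only add to the number counted. The size is not computable, because the documents give no baseline prevalence for any of these limits; the percentages above only show how sensitive the rows could be. This should be corrected, since the SAP already uses the needed convention elsewhere.

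**What to change.** In SAP Sections 2.8.1.1, 2.8.3 and 2.8.4.2:

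1. Add post-baseline to the eGFR bullet in Table 2-3.
2. Report the affected rows by baseline status, as already done for treatment-emergent hyperkalemia. Give n/m (%), where m is the patients with a baseline value not meeting the threshold and at least one post-baseline value. Show patients who met it at baseline on a separate line. The all-patient count may stay alongside.
3. Leave rows where entry criteria exclude baseline cases (eGFR below 30, numeric ALT/AST criteria) as they are.

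In the protocol, reconcile the title of Table 3-1 with the text of Section 3 on whether its criteria apply at Visit 501. That decides whether the potassium and 5th-percentile SBP rows need the same treatment.

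The cost is SAP wording and programming, with no new data. Denominators will differ by row, and patients without a baseline value leave the conditioned rows.
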